9.7.2.2. Secondary Efficacy Analyses

9.7.2.2.1. NRS "average pain over past 24 hours" intensity scores from first pain assessment post-treatment (Day 1) to Day 30, Day 180, and Day 360

Analysis and presentation will be the same as that of the primary analysis for the primary efficacy endpoint as outlined in **Section 9.7.2.1.1**.

9.7.2.2.2. Changes in NRS pain intensity scores (“average pain over 24 hours) from pre-treatment until Day 360

The percent changes will be calculated for each subject as follows:

$$\% \text{ Change} = \{NRS_{\text{current}} - NRS_{\text{screening}}\} / NRS_{\text{screening}} \times 100\%.$$

The current pain will be used at each post-treatment visit, and the change of NRS current pain will be defined as post iovera^o/RFA - pre iovera^o/RFA. Analysis and presentation will be the same using percent changes as an outcome as that of the primary analysis for the primary efficacy endpoint as outlined in **Section 9.7.2.1.1**. However, the regression model will not incorporate adjustments for covariates.

9.7.2.2.3. Oswestry Disability Index scores from Day 30 to Day 360

Analysis and presentation will be the same as that of the primary analysis for the primary efficacy endpoint as outlined in **Section 9.7.2.1.1**.

9.7.2.2.4. Change in Oswestry Disability Index (ODI) scores from pre-treatment to Day 360

Analysis and presentation will be the same as that of the primary analysis for the primary efficacy endpoint as outlined in **Section 9.7.2.1.1**.

9.7.2.2.5. Patient’s Global Impression of Change (PGIC) from Day 30 to Day 360

Analysis and presentation will be the same as that of the primary analysis for the primary efficacy endpoint as outlined in **Section 9.7.2.1.1**.

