9.7.1.2. Secondary Endpoints

The following endpoints are secondary efficacy endpoints:

- NRS "average pain over past 24 hours" intensity scores from first pain assessment post-treatment (Day 1) to Day 30, Day 180, and Day 360
- Changes in NRS pain intensity scores ("average pain over 24 hours") from pre-treatment to Day 360
- Oswestry Disability Index scores (ODI) from Day 30 to Day 360
- Change in Oswestry Disability Index (ODI) scores from pre-treatment to Day 360
- Patient's Global Impression of Change (PGIC) scores from Day 30 to Day 360
- Patient satisfaction with pain management from Day 30 to Day 360
- Percentage of subjects who are in "no disability" determined by ODI scores at Day 360
- Concomitant medication use

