9.7.2.1. Primary Efficacy Analysis

9.7.2.1.1. NRS "average pain over past 24 hours" Intensity Score scores from first pain assessment post-treatment (Day 1) to Day 360

The primary analysis of the primary efficacy endpoint will compare the iovera^o and RFA group. The superiority of iovera^o to RFA will be evaluated based on the following null hypothesis and alternative hypothesis:

H₀: iovera^o is not superior to RFA with respect to mean of NRS pain intensity scores at Day 360

H_a: iovera^o is superior to RFA with respect to mean of NRS pain intensity scores at Day 360

A two-sided hypothesis test will be performed at $\alpha=0.05$ level of significance comparing EXPAREL and bupivacaine HCl as follows:

- If the two-sided p-value for the least squares mean treatment difference in NRS at Day 360 (iovera^o- RFA) is >0.05 , then the superiority of iovera^o to RFA is not achieved.
- If the p-value for the least squares mean treatment difference in NRS at Day 360 (iovera^o- RFA) is ≤ 0.05 , then the superiority of iovera^o to RFA is achieved.

Least Squares Means (LSM) of “average pain over 24 hours” at Day 360 will be calculated for each subject. LSM for “average pain over 24 hours” at Day 360 will be summarized by treatment group, and overall.

To test for significant differences between iovera^o and RFA group, a Linear Regression Model with adjustment of baseline NRS, sex, and tobacco status was used. The LS means for each treatment group, two-sided 95% CI for the LS mean difference, and p-value will be presented.

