10. SAMPLE SIZE CALCULATIONS

As the aim of this pilot study is not to assess effectiveness or efficacy, formal hypothesis testing will not be determined, and sample size will not be calculated based on desired statistical power to detect a treatment effect. A total of 30 subjects are planned for this pilot study, with 15 randomized to each of the 2 study groups.

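### SAP 9.7.2.2 carries the primary analysis, which includes a two-sided 0.05 superiority rule, to the modelled secondary endpoints with no ordering, alpha control or nominal label, although the protocol and SAP Section 10 disclaim formal testing

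*SAP*

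**What the plan says.** SAP 9.7.2.1.1 sets out the primary analysis of average pain over 24 hours. "A two-sided hypothesis test will be performed at $\alpha=0.05$ level of significance", and if the p-value for the Day 360 difference is at most 0.05, "then the superiority of iovera^o to RFA is achieved". On the model, it says that "a Linear Regression Model with adjustment of baseline NRS, sex, and tobacco status was used". LS means, the 95% CI for their difference and a p-value are to be presented.

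SAP 9.7.2.2.1 to 9.7.2.2.5 cover five secondary items. Each is to be handled as the primary is: "Analysis and presentation will be the same as that of the primary analysis for the primary efficacy endpoint as outlined in" Section 9.7.2.1.1. (Section 9.7.2.2.2 words this slightly differently, with percent change as the outcome.) The items are:

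- NRS average pain, "intensity scores from first pain assessment post-treatment (Day 1) to Day 30, Day 180, and Day 360"
- percent change in NRS, with one exception: "However, the regression model will not incorporate adjustments for covariates"
- ODI from Day 30 to Day 360
- change in ODI to Day 360
- PGIC from Day 30 to Day 360

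The other secondary endpoints in SAP 9.7.1.2 (satisfaction, the no-disability percentage, concomitant medication) get no model in 9.7.2.2.

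SAP Section 10 says of the whole study: "formal hypothesis testing will not be determined, and sample size will not be calculated based on desired statistical power to detect a treatment effect". The protocol's Statistical Methods say the same. SAP 9.7.2 promises descriptive statistics for both the primary and the secondary efficacy analyses.

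**The concern.** The primary analysis includes a decision rule as well as a model. If its analysis and presentation are copied to the secondaries without qualification, a programmer or report author can fairly attach the same superiority verdict to each of them. Nothing readable in 9.7.2.2 says which result counts if they differ, or that the p-values are nominal.

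One outcome is also analysed in two ways. Average pain appears as a covariate-adjusted score and as an unadjusted percent change from screening. The percent-change section is itself unclear: its title refers to average pain, but its text says current pain is used at each visit. If the two analyses disagree, no rule says which stands.

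The pilot is meant to inform a full efficacy trial and its sample size. A chance finding on one scale or at one visit, reported as superiority, could influence that trial's endpoint and time point.

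**Working it through.** **Inputs.** The per-test level is 0.05 two-sided (SAP 9.7.2.1.1). The sample is 30 subjects, 15 per arm (SAP Section 10), and is not based on power. The documents give no correlations between endpoints, so every correlation below is an assumption.

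**The plan's own figure.** For one test, 1 − (1 − 0.05) = 0.05. By symmetry, half of this (0.025) lies in the direction favouring iovera.

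**Counting tests.** Take percent change, ODI, ODI change and PGIC once each, at Day 360. The Day 360 NRS entry in 9.7.2.2.1 repeats the primary and adds nothing. That leaves NRS at Days 30, 180 and 360, percent change, ODI, ODI change and PGIC, which is 7 tests including the primary.

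The count is 6 if ODI score and ODI change are both adjusted for baseline ODI. Change is score minus baseline. With baseline in the model, only the baseline coefficient shifts (by 1), so the treatment estimate and its p-value are identical. The covariate actually listed is baseline NRS. With that alone, the two ODI analyses are distinct tests.

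**Independent tests.**

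- Any p ≤ 0.05, seven tests: 1 − 0.95^7 = 0.3017
- Any p ≤ 0.05, six tests: 1 − 0.95^6 = 0.2649
- Any such result favouring iovera, seven tests: 1 − 0.975^7 = 0.1624
- Any such result favouring iovera, six tests: 1 − 0.975^6 = 0.1409

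**Correlated tests.** Let Z_i = √ρ·C + √(1−ρ)·E_i, with C and E_i independent standard normal. Count trials in which any |Z_i| > 1.96, and separately those in which any Z_i < −1.96 (favouring iovera). This used 400,000 draws for each value of ρ. The ρ = 0 row comes from the formulas above.

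| Assumed ρ | 7 tests, any p ≤ 0.05 | 7 tests, favouring iovera | 6 tests, any p ≤ 0.05 | 6 tests, favouring iovera |
|---|---|---|---|---|
| 0 | 0.3017 | 0.1624 | 0.2649 | 0.1409 |
| 0.3 | 0.2704 | 0.1368 | 0.2412 | 0.1212 |
| 0.5 | 0.2288 | 0.1149 | 0.2073 | 0.1036 |
| 0.7 | 0.1780 | 0.0890 | 0.1641 | 0.0815 |
| 0.9 | 0.1141 | 0.0575 | 0.1078 | 0.0539 |

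**Cross-check with the SAP's models.** I simulated trials with 15 per arm and no treatment effect, 6,000 per scenario. All seven analyses were adjusted for baseline NRS, sex and tobacco use, except percent change, which was unadjusted. Each single test rejected in 4.4% to 5.7% of trials. At least one of the seven rejected in 19.0% of trials with strong assumed correlations (0.7 to 0.8), 25.2% with correlations of 0.3, and 26.3% when nearly uncorrelated. Counting only results favouring iovera gave 9.5% to 14.4%. These agree with the table.

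**The case against.** The strongest reply is that the superiority verdict on secondaries is an inference. The hypotheses and both decision bullets in 9.7.2.1.1 name only NRS at Day 360. What 9.7.2.2 carries over could be just the model, LS means, CI and p-value. That reading is possible, so it cannot be said that the SAP definitely declares superiority on ODI, PGIC or earlier pain scores. Carry-over is still the natural reading, since the rule is part of the analysis referred to and no text excludes it.

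It can also be said that the protocol and SAP Section 10 already settle the matter, so that no family of tests remains. Those statements do limit the whole study, and SAP 9.7.1 does name one primary endpoint. But 9.7.2.1.1 and 9.7.2.2 are the specific instructions that will be executed. SAP 9.7 says descriptive statistics will also be shown, which implies that they accompany other analyses. The general statement contradicts the specific ones without switching them off, and it labels no secondary exploratory.

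A reader might infer more than the documents support, in four ways:

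- **A false superiority call is 4 to 5 times as likely as stated.** The 5% is a per-test level, and no familywise rate is promised. The multiple runs from 2.3 (0.1141/0.05) to 6.0 (0.3017/0.05), depending on an assumed correlation. It also counts results favouring RFA, which qualify only because the rule has no sign condition.
- **ODI is tested twice with different models.** Sections 9.7.2.2.3 and 9.7.2.2.4 use the same model. Only percent change drops the covariates.
- **There are about 29 tests.** That count expands ODI and PGIC to 12 visits each but leaves percent change at one, although its section mentions each post-treatment visit. Visit-by-visit testing would raise the figures, but the text does not fix a number.
- **Secondary p-values will drive the decision on the full trial.** The study-success criteria in SAP 9.6.4 are redacted, so this cannot be seen.

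**Conclusion.** The point holds as a gap in the SAP and a conflict between its sections. Section 9.7.2.2 extends an analysis containing a 0.05 superiority rule to the modelled secondaries without order, alpha control or a nominal label, while Section 10 and the protocol disclaim formal testing.

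The size depends on three assumptions: that the rule carries over, that percent change, ODI, ODI change and PGIC are each tested once at Day 360, and that the tests share a common correlation. For seven tests at 0.5, the chance of at least one p ≤ 0.05 under no difference is about 23% (range about 11% to 30%), against 5% for one test. For results favouring iovera, which is the cleaner comparison, it is about 11.5% (about 6% to 16%), against 2.5%. With six tests the overall range is about 11% to 26%. This is worth correcting before analysis. It does not show that the SAP breaks a stated error guarantee, because it makes none.

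**What to change.** First reconcile 9.7.2.1.1 with SAP Section 10 and the protocol's Statistical Methods, and decide whether the 0.05 rule stays at all. Then make these changes:

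- In 9.7.2.2, replace the cross-reference to the primary analysis with wording such as: *The regression model will be used for estimation only. LS means, their difference and its two-sided 95% CI will be shown. Any p-value is nominal, with no adjustment for multiplicity. The superiority rule in 9.7.2.1.1 does not apply to secondary endpoints.*
- In 9.7.2.1.1, state that the rule, if kept, applies only to the covariate-adjusted difference in average-pain NRS at Day 360.
- State that the percent-change and ODI-change analyses are supportive and cannot override the corresponding score analysis. Say whether percent change uses average or current pain, and whether the baseline covariate for ODI is baseline NRS or baseline ODI.
- Delete the repeated Day 360 entry from 9.7.2.2.1.

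The cost is a few sentences of SAP text, with no new data or subjects. The sponsor gives up superiority statements on secondary endpoints, which Section 10 and the protocol already say this pilot does not seek.

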- 1. Male or female volunteers, at least 18 years of age at screening
- 2. Primary complaint of axial low-back pain suggestive of unilateral or bilateral facet joint involvement (i.e., facet mediated CLBP)
- 3. Low back pain is chronic (i.e., > 3 months' duration)
- 4. Low back pain score of \geq 4 (i.e., moderate pain) on the 0 to 10 NRS or functional impairment at screening
- 5. Successful trial of two diagnostic medial branch blocks consisting of two positive blocks with local anesthetic only (i.e., no steroids) that results in at least 50% relief of primary (index) pain for the duration of the local anesthetic used or history of a positive response to prior radiofrequency treatment (i.e., ≥ 6 months prior to enrollment)
- 6. Failure of at least three months of conservative non-operative therapy (e.g., physical therapy, chiropractic care, spinal injections, NSAIDs or other appropriate analgesics),
- 7. Able to provide informed consent, adhere to the study visit schedule, and complete all study assessments

Exclusion Criteria:

Subjects who meet any of the following exclusion criteria will not be eligible for participation in this study:

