Appendix 1: Subject's Reported Pain (Numeric Rating Scale)

Subjects will evaluate their pain in the low back region using an 11-point Numeric Rating Scale (NRS), where 0=no pain and 10=worst possible pain.

The timepoints and assessments are as follows:

Current Pain (Pain "right now")	Daily Pain (Worst/Average pain over 24 hours)
At screening	At screening
Day of iovera° or RFA treatment (pretreatment), once daily Days 1-6 (at 6 pm ±4 hours) after treatment, at Day 7 (± 2 days), Day 15 (± 2 days), Day 30 (± 5 days), Day 60 (± 5 days), Day 90 (± 5 days), Day 120 (± 5 days), Day 150 (± 5 days), Day 180 (± 5 days), Day 210 (± 7 days), Day 240 (± 7 days), Day 270 (± 7 days), Day 300 (± 7 days), Day 330 (± 7 days), Day 360 (± 7 days)	Once daily Days 1-6 (at 6 pm ±4 hours) after treatment, at Day 7 (± 2 days), Day 15 (± 2 days), Day 30 (± 5 days), Day 60 (± 5 days), Day 90 (± 5 days), Day 120 (± 5 days), Day 150 (± 5 days), Day 180 (± 5 days), Day 210 (± 7 days), Day 240 (± 7 days), Day 270 (± 7 days), Day 300 (± 7 days), Day 330 (± 7 days), Day 360 (± 7 days)

**Current Pain:** Subjects will evaluate how much pain they are currently experiencing (i.e., "How much pain are you experiencing in your low back **right now**?") at Screening, day of iovera^o treatment (pretreatment), once daily (at 6 pm ±4 hours) from prior to iovera^o treatment to Days 1-6, at Day 7 (\pm 2 days), Day 15 (\pm 2 days), Day 30 (\pm 5 days), Day 60 (\pm 5 days), Day 90 (\pm 5 days), Day 120 (\pm 5 days), Day 150 (\pm 5 days), Day 180 (\pm 5 days), Day 210 (\pm 7 days), Day 240 (\pm 7 days), Day 270 (\pm 7 days), Day 300 (\pm 7 days), Day 330 (\pm 7 days), Day 360 (\pm 7 days):

Pain Intensity Scale (Current Pain)

On a scale of 0 to 10, where 0 = no pain and 10 = worst possible pain, circle the number that best describes your answer to the question "How much pain are you experiencing in your low back **right now**?" (Circle one number only.)

0 1 2 3 4 5 6 7 8 9 10

No pain

Worst possible pain

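### SAP 9.7.2.2.2 tests unadjusted percent change from screening NRS, which is undefined at a score of 0 and unstable at 1 or 2, and the entry criteria allow such scores

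*SAP*

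**What the plan says.** SAP 9.7.1.2 lists change in average-pain NRS "from pre-treatment to Day 360" as a secondary efficacy endpoint. SAP 9.7.2.2.2 gives its analysis:

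- **Metric.** "The percent changes will be calculated for each subject as follows": current NRS minus screening NRS, divided by screening NRS, times 100.
- **Model.** "Analysis and presentation will be the same using percent changes as an outcome as that of the primary analysis", so the two-sided test of SAP 9.7.2.1.1 at 0.05 carries over.
- **Adjustment.** "However, the regression model will not incorporate adjustments for covariates".
- **Absolute change.** The section also defines a post-minus-pre change in points, but does not attach the model to it.

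The other modelled NRS analyses (9.7.2.1.1 and 9.7.2.2.1) adjust for baseline NRS, sex and tobacco status. The ODI change analysis (9.7.2.2.4) refers to the primary method without this exception.

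Protocol inclusion criterion 4 sets a low back pain score of at least 4 and continues "i.e., moderate pain) on the 0 to 10 NRS or functional impairment at screening". It does not say which NRS item has to reach 4. Protocol Appendix 1 describes pain scored "using an 11-point Numeric Rating Scale (NRS), where 0=no pain and 10=worst possible pain", so 0 is a valid score. Neither document has a rule for a zero or very small denominator. The missing-data rule in SAP 9.1.1.1 covers dropouts only.

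**The concern.** A ratio to baseline behaves well only when baselines are comfortably above zero. The functional-impairment branch of criterion 4 removes that guarantee. So does the unnamed NRS item: a subject may qualify on one item and have a lower score on the item used as the denominator.

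Two things are at stake. A subject with a screening score of 0 has no value for this outcome and falls out of the analysis, although SAP 9.7.2 places all efficacy analyses on the efficacy analysis set. And improvement stops at -100% while worsening from 1 or 2 can run to several hundred percent, so one such subject can dominate the mean, the SD and the p-value of a small arm.

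**Working it through.** **Inputs from the documents.** Formula: SAP 9.7.2.2.2. Scale 0 to 10: Protocol Appendix 1. Arm size: "A total of 30 subjects are planned for this pilot study, with 15 randomized to each of the 2 study groups" (SAP section 10). The plan gives no SD, effect size or power for this endpoint, so there is no figure of its own to reproduce.

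**Step 1: range of the metric.** Percent change = 100 × (post - screening) / screening. This step needs no assumption.

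| Screening NRS | Lowest | Highest (post = 10) | Value of one point |
|---|---|---|---|
| 0 | undefined | undefined | undefined |
| 1 | -100% | (10-1)/1 = +900% | 100 percentage points |
| 2 | -100% | (10-2)/2 = +400% | 50 |
| 3 | -100% | (10-3)/3 = +233% | 33 |
| 4 | -100% | (10-4)/4 = +150% | 25 |
| 6 | -100% | (10-6)/6 = +67% | 17 |

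**Step 2: one subject in an arm of 15.** Assume that the other 14 go from 6 to 3 (-50%, -3 points). The fifteenth worsens by 4 points in every row.

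| Fifteenth subject | Percent change | Arm mean, percent | Arm mean, points |
|---|---|---|---|
| 1 to 5 | +400% | (14×(-50)+400)/15 = -20.0% | (14×(-3)+4)/15 = -2.53 |
| 2 to 6 | +200% | (14×(-50)+200)/15 = -33.3% | -2.53 |
| 3 to 7 | +133% | (14×(-50)+133.3)/15 = -37.8% | -2.53 |
| 6 to 10 | +67% | (14×(-50)+66.7)/15 = -42.2% | -2.53 |

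The same worsening counts equally in points, but by very different amounts in percent. For a two-point worsening, 3 to 5 gives -42.2% and an ordinary 6 to 8 gives -44.4%, so baseline 3 is not far out of line. A low-baseline subject who improves does little: 1 to 0 gives (14×(-50)-100)/15 = -53.3%. A screening score of 0 costs 1/15 = 6.7% of an arm.

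**Step 3: effect on the test.** Take an assumed 15 v 15 data set with mean percent changes of -50% and -20% and SD 15.8. The unadjusted t-test, which is the no-covariate regression, gives p = 0.00002. Replace one -50% value in the better arm with a 1-to-5 subject (+400%). That arm's SD rises to 117, the means become -20% v -20%, and p = 1.0; the arm's median stays at -50%. With a 2-to-4 subject p = 0.09; with a 4-to-6 subject p = 0.013.

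**Step 4: average behaviour.** This is a simulation of 4,000 trials per scenario. Assumed: true difference 2 points, residual SD 2, baselines 4 to 9, low-baseline subjects at 1 to 3. The comparator is raw follow-up NRS adjusted for baseline.

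| Low-baseline subjects of 30 | Power, unadjusted percent change | Power, baseline-adjusted raw NRS |
|---|---|---|
| 0 | 71% | 73% |
| 1 | 65% | 72% |
| 2 | 61% | 72% |
| 4 | 55% | 72% |
| 6 | 52% | 72% |

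With no true effect, the percent-change test rejected in about 3% to 5% of trials. The simulated effect is constant in points, which favours the points model, so the power figures are illustrative.

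**The case against.** The strongest case on the other side has five parts.

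- **Safeguards already planned.** SAP 9.7.2 asks for medians as well as means, and 9.7.2.2.2 already defines the change in points. Baseline-adjusted raw average-pain models are planned for Days 30, 180 and 360. This stands, and it limits the damage: conclusions about pain do not rest on the percent-change test alone.
- **Rarity.** Entry also needs a primary complaint of axial low back pain, failed conservative therapy, and two positive blocks or an earlier response to radiofrequency treatment. A screening score of 0 is therefore improbable. This stands too, but criterion 4 still admits scores of 0 to 3, and the plan says nothing about them.
- **A covariate is not the cure.** Adding baseline to the percent-change model would leave the zero denominator and the lopsided scale in place. This is correct, so the outcome has to change and not only the adjustment.
- **Reach of the distortion.** A reader might infer that the arm means would reflect baseline scores in place of pain relief, or that false positives would rise. The documents and the working do not support either. The distortion needs a subject at 1 or 2 who worsens substantially, and the simulated type I error did not rise.
- **Sizing the next trial.** A reader might infer that the SD used to size the full RCT would be inflated. The protocol says only that the pilot should provide a basis for a sample-size calculation. No document names the percent-change SD for that purpose, and raw NRS SDs will be reported as well.

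**Conclusion.** The point holds as a weakness in a secondary analysis. Followed as written, SAP 9.7.2.2.2 gives no value for a subject with a screening score of 0. Its arm mean of 15 can move by 30 percentage points through one subject going from 1 to 5, against about half a point on the NRS. The ranges by screening score follow from the SAP formula alone. The influence, p-value and power figures rest on the assumptions stated with them. The number of subjects who will enter with a score of 0 to 3 cannot be determined from the documents; if there are none, the low-baseline problem does not arise. The effect is modest at a score of 3, and there is no comparable distortion for subjects who improve. The cost is lost precision, an unstable mean and possibly a lost subject. The primary endpoint is untouched.

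**What to change.** In SAP 9.7.2.2.2, assign the regression to the post-minus-pre change in points, with the covariates of 9.7.2.1.1: baseline NRS, sex and tobacco status. Present percent change descriptively only, by its median, and state how many subjects have a screening score of 0 and so no computable value.

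The same edit should settle which pain item and which pre-treatment value are meant. The section's title says average pain while its text uses current pain. The formula uses screening, while SAP section 7 takes the last value before treatment as baseline.

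The cost is SAP wording; the data are already collected. There are two downsides. Mean percent change is no longer a tested result. And for average pain at Days 30, 180 and 360 the adjusted contrast will coincide with the raw-score models already planned: if post - pre = a + d×treatment + b×pre + other terms, then post = a + d×treatment + (b+1)×pre + the same terms, with the same d. This assumes the same subjects, and that the pre-treatment value subtracted is also the baseline covariate.

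A proportion with at least 50% reduction could be added descriptively, but it is optional. The protocol uses 50% as an eligibility threshold for diagnostic blocks and not as a definition of treatment success. A change from 2 to 1 would count as a response, and the study-success section (SAP 9.6.4) is redacted, so it cannot be said whether a success rate is already defined there.

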Randomization to treatment groups according to the randomization assignment will be performed on the day of treatment. The treatment groups are:

Name of Device:

iovera° System

- **Group 1:** subjects will receive iovera° cryoneurolysis to the medial branch nerves of the lumbar spine
- **Group 2:** subjects will receive RFA to the medial branch nerves of the lumbar spine

Screening

Subjects will be screened within 30 days of the scheduled iovera^o medial branch cryoneurolysis or RFA procedure to determine their eligibility. Subjects must provide informed consent – as documented in a study informed consent form (ICF) before performing any study related procedure that differs from the standard of care (SOC) at the study site.

During the screening visit, subjects will be assessed for past or present neurologic and general medical conditions that in the judgment of the Investigator would preclude them from study participation. No procedures other than the site's SOC will be performed before signed informed consent is obtained. After the ICF is signed, demographic information, medical and surgical history, concomitant medications/concurrent procedures information, and vital signs will be collected. Assessment of the intended treatment areas will be conducted. Subjects will assess their pain in the low back region using the Numeric Rating Scale (NRS). Subjects must be instructed to report any adverse device effects and adverse events (AEs) to the Investigator from the time the ICF is signed through Day 360 (±7 days).

When screening test results are received and the subject is deemed eligible for the study, the subject will be notified that he or she is enrolled in the study.

Method of Assigning Subjects to Treatment

Randomization scheme

This is a randomized pilot study. The study will enroll 30 total subjects 1:1 to receive iovera^o medial branch cryoneurolysis or radiofrequency ablation on the day of treatment.

The randomization code will be computer generated.

Randomization Procedures

Once a subject is identified as being qualified for the study in accordance with the eligibility criteria, the Investigator or designee will obtain a randomization assignment on the day of treatment. The subject will be considered randomized into the study once the study treatment is assigned.

Replacement of Subjects

Name of Device: iovera° System

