Daily Pain: Subjects will evaluate their *worst* and *average* level of pain over the past 24 hours at Screening, once daily (at 6 pm ±4 hours) from prior to iovera° treatment to Day Days 1-6, at Day 7 (\pm 2 days), Day 15 (\pm 2 days), Day 30 (\pm 5 days), Day 60 (\pm 5 days), Day 90 (\pm 5 days), Day 120 (\pm 5 days), Day 150 (\pm 5 days), Day 180 (\pm 5 days), Day 210 (\pm 7 days), Day 240 (\pm 7 days), Day 270 (\pm 7 days), Day 300 (\pm 7 days), Day 330 (\pm 7 days), Day 360 (\pm 7 days):

```
CONFIDENTIAL
```

Pain Intensity Scale (Daily Pain)

On a scale of 0 to 10, where 0 = no pain and 10 = worst possible pain, circle the number that best describes your answer to the question "What was your **worst** pain in the past 24 hours in your low back?" (Circle one number only.)

0 1 2 3 4 5 6 7 8 9 10

No pain

Worst possible pain

On a scale of 0 to 10, where 0 = no pain and 10 = worst possible pain, circle the number that best describes your answer to the question "What was your **average** pain in the last 24 hours in your low back?" (Circle one number only.)

0 1 2 3 4 5 6 7 8 9 10

No pain

Worst possible pain

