7. DEFINITIONS

Diagnostic Medial Branch Block (MBB)

As part of the eligibility criteria, subjects must have undergone two successful diagnostic medial branch blocks consisting of two positive blocks with local anesthetic only (i.e., no steroids) under fluoroscopic guidance that results in at least 50% relief of primary (index) pain for the duration of the local anesthetic used.

Treatment-emergent Adverse Events

Treatment-emergent adverse events (TEAEs) are adverse events started on/after the start of iovera^o treatment.

Baseline

Baseline is defined as the last available measurement or assessment prior to the start of study treatment.

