9.4.2. Baseline Characteristics

The summary of baseline characteristic data will present:

- Body Mass Index (BMI) (kg/m²)
- Tabaco use status
- NRS current pain intensity score (pain “average”)
- Duration of having diagnosed with low back pain (years)
- Oswestry Disability Index

Baseline characteristics summaries will present the data for each treatment group. Descriptive statistics (n, mean, SD, median, minimum and maximum) will be provided for continuous variables. The number and percent of subjects will be tabulated for the categorical variables.

Baseline characteristic data will be summarized and listed using the safety analysis set.

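### The NRS change analysis in SAP 9.7.2.2.2 names current pain for an average-pain endpoint, and neither ODI analysis adjusts for baseline ODI

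*SAP*

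**What the plan says.** **NRS change.** SAP 9.7.1.2 lists the endpoint as "Changes in NRS pain intensity scores ('average pain over 24 hours') from pre-treatment to Day 360", and the heading of 9.7.2.2.2 names the same item. The text beneath gives a percent-change formula with the screening score as divisor, then says "The current pain will be used at each post-treatment visit, and the change of NRS current pain will be defined as post" minus pre-treatment. Percent change is the modelled outcome, without covariates. SAP Section 7 states: "Baseline is defined as the last available measurement or assessment prior to the start of study treatment".

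Protocol Appendix 1 treats current pain as its own question ("Subjects will evaluate how much pain they are currently experiencing"), separate from the worst and average scores over 24 hours. SAP 9.4.2 mixes the two labels: "NRS current pain intensity score (pain “average".

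**ODI.** SAP 9.7.2.2.3 (scores) and 9.7.2.2.4 (change) both refer to the analysis of 9.7.2.1.1, a linear regression adjusted for baseline NRS, sex and tobacco status and tested two-sided at 0.05. Neither states an exception, whereas 9.7.2.2.2 does state one. The ODI is completed at screening (Protocol Appendix 3) and tabulated as a baseline characteristic (SAP 9.4.2).

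**The concern.** The SAP should let two programmers produce the same number. In 9.7.2.2.2 one could take average pain from the heading and the other current pain from the method. The choice of item also affects the reference value: current pain is scored at screening and again on the treatment day, and "Subjects will be screened within 30 days of the scheduled" procedure, so the two scores can be weeks apart. Percent change also has no value when the divisor is 0 and is unstable when it is small. The SAP has no rule for this, and Inclusion Criterion 4 admits subjects on functional impairment alone, so low scores are possible. How often they occur is unknown.

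For ODI, the baseline of the outcome itself is usually its strongest available predictor. If it is left out, chance baseline imbalance stays in the estimates, and one Day 360 outcome can give two different treatment differences.

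**Working it through.** The documents give no SD, effect size or power, so there is no plan figure to reproduce. ODI SDs, correlations and effect sizes below are assumptions.

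**1. Which pre-treatment scores exist**

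| Item | Source | Before treatment |
|---|---|---|
| Current pain | Protocol Clinical Assessments; Appendix 1 | Screening and treatment day |
| Average pain | Appendix 1 table | Screening only; then "once daily Days 1-6 (at 6 pm ±4 hours) after treatment" |
| Average pain | Protocol Clinical Assessments | Days 1-6 scores are after treatment |
| Average pain | Protocol Table 1, as far as the extracted table can be read | Screening mark, treatment-day cell blank |
| Average pain | Appendix 1, Daily Pain text | Screening, then "once daily (at 6 pm ±4 hours) from prior to iovera° treatment to Day Days 1-6" |

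Three places agree that average pain has only a screening score before treatment. On that schedule the screening divisor, the pre-treatment value and the Section 7 baseline are the same number. Only the Daily Pain text leaves room for another, and its wording nearly repeats the Current Pain sentence.

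**2. What the reference and divisor can do (illustrative scores)**

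- Day 360 score 3, screening 6: (3 − 6)/6 = −50%. With a treatment-day score of 4: (3 − 4)/4 = −25%. This can arise for current pain, or for average pain only if the Daily Pain text governs.
- A 2-point change in one subject shifts a 15-subject arm mean by (2/divisor) × 100/15 percentage points: 13.3 at divisor 1, 6.7 at 2, 2.2 at 6; undefined at 0.

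**3. ODI score against ODI change**

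With the same subjects and covariates, least squares is linear in the outcome, so

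score difference − change difference = covariate-adjusted baseline ODI difference between arms.

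If baseline ODI is itself a covariate, the right-hand side is exactly zero.

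Let ρ be the correlation of baseline with Day 360 ODI, r that of baseline NRS with Day 360 ODI, and c that of baseline NRS with baseline ODI. The SD of the gap is SD × √(1 − c²) × √(2/15). At SD 15 and c = 0.3: 15 × 0.954 × 0.365 = 5.2 points. Over c = 0.2 to 0.5 it is 3.2-3.6 points at SD 10, 4.7-5.4 at SD 15 and 6.3-7.2 at SD 20. Simulation with sex and tobacco status in the model (50% and 25% assumed) gives 4.9-5.8 at SD 15, with the gap above 5 points in 31-39% of trials.

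For scale, the 95% CI half-widths at SD 15 and r = c = 0.3, with t(25) = 2.060, are:

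- score: 2.060 × 15 × √(1 − 0.09) × 0.365 = 10.8;
- change: 2.060 × 15 × √(2(1 − ρ)) × 0.365 = 13.3, 11.3 and 8.7 at ρ = 0.3, 0.5, 0.7.

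The two planned ODI tests disagree at 0.05 in 7-9% of simulated trials with no true effect, 19-33% at 0.5 SD and 30-37% at 0.8 SD. With baseline ODI in the model they never disagree.

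**4. Precision**

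Residual variance in SD² units at r = c = 0.3. As written: score 1 − r² = 0.91; change 2(1 − ρ). With baseline ODI added: (1 − r² − c² − ρ² + 2ρrc)/(1 − c²) for both outcomes.

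| ρ | As written, score | As written, change | Baseline ODI added | Cut, score | Cut, change |
|---|---|---|---|---|---|
| 0.3 | 0.91 | 1.40 | 0.784/0.91 = 0.862 | 5% | 38% |
| 0.5 | 0.91 | 1.00 | 0.66/0.91 = 0.725 | 20% | 27% |
| 0.7 | 0.91 | 0.60 | 0.456/0.91 = 0.501 | 45% | 16% |

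**5. Add or swap**

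Replacing baseline NRS with baseline ODI changes the score variance by the factor (1 − ρ²)/(1 − r²). At ρ = 0.3 and r = 0.5 that is 0.91/0.75 = 1.21, a 21% loss. Simulated standard errors of the score difference there, in SD units, are 0.331 as written, 0.365 with the swap and 0.332 with both. At ρ = 0.5 and r = 0.3 they are 0.365, 0.331 and 0.334. Adding protects against the bad case at almost no cost in the good one.

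**The case against.** - **The wording is only loose.** In the formula, the subscript for current may mean the current visit, 9.4.2 attaches the same word to the average item, and the endpoint list and heading both say average. This largely stands, and a reader should not infer that a different item was deliberately chosen. But the sentence after the formula names current pain twice, which is the protocol's name for another question, so the words need correcting.
- **The reference value.** A reader might infer that the reference for average pain is unresolved and that the protocol must be amended first. The documents do not support that. Three of four places schedule only a screening score, and the Section 7 rule gives one value on either schedule.
- **The ODI estimates.** A reader might infer that they are biased. They are not: under randomization, score and change are both valid, and the change outcome already subtracts baseline ODI. What remains is precision, chance imbalance and two answers to one question.
- **This is a pilot without formal testing.** SAP Section 10 says so, yet 9.7.2.1.1 plans a 0.05-level test that the ODI sections inherit. If those tests are dropped, the disagreement rates lose their force. The gap between the two estimates remains.

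**Conclusion.** The point holds, with modest consequences. SAP 9.7.2.2.2 names the wrong item for its endpoint. Once the item is corrected to average pain, the screening divisor and the Section 7 baseline coincide unless the Daily Pain text is followed. Baseline ODI is a covariate in no model. At an assumed ODI SD of 15 this leaves a gap with an SD of about 5 to 6 points between the Day 360 score and change results, typically inside either confidence interval. The existence of the gap, and its removal by including baseline ODI, follow from algebra and need no assumption beyond the same subjects in both models. Its size, the precision gains and the disagreement rates rest on the assumed SDs, correlations and effects. These are secondary analyses in a 30-subject pilot, and the descriptive summaries of ODI are not affected.

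**What to change.** **(a) SAP 9.7.2.2.2.** Replace current pain with average pain over 24 hours at both the pre- and post-treatment times. Use the Section 7 baseline as the single reference for percent and absolute change. State that percent change is not calculable when the baseline is 0, and report how many subjects this affects. The unadjusted percent-change model can stay. No protocol change is required, though the Appendix 1 table and Daily Pain text should be reconciled when convenient.

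**(b) SAP 9.7.2.2.3 and 9.7.2.2.4.** Add baseline ODI to the 9.7.2.1.1 covariates and report the Day 360 score and change treatment differences as one result. Replacing baseline NRS instead is acceptable, but can lose precision if the own-baseline ODI correlation is low.

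**Cost.** SAP wording and one degree of freedom (25 to 24 with 30 subjects and two-level sex and tobacco status). No new data are needed, since the ODI is already collected at screening.
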